2.3 Rationale for dose and regimen selection

Patients enrolled in this study will receive 125 mg qd of Infigratinib on a 3 week on (21 day) /1 week off (7 day) schedule in 28-day cycles. This dose level and regimen is based on experiences from the CInfigratinibX2101 trial.

The MTD/RP2D from the CInfigratinibX2101 study was identified as 125 mg administered once daily (qd) in continuous 28-day cycles. While dose levels of 100 mg qd and higher were tolerated by patients, the majority of the patients experienced reversible hyperphosphatemia, which led to study drug interruptions. An evaluation of the drug administration records for patients prior to receiving prophylactic phosphate-lowering therapy, indicated that the median time until first dose interruption was approximately 23 days and the median duration of interruption was 7 days. This observation led to the introduction of an expansion arm in the ongoing CInfigratinibX2101 study to evaluate the administration of 125 mg qd on a 3 week on (21 days) / 1 week off (7 days) schedule in 28-day cycles. To date, the majority of patients enrolled in this arm have completed their first cycle of therapy without hyperphosphatemia induced dose interruptions, while maintaining anti-tumor activity.

3. Objectives and endpoints

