6.1.2 Ancillary treatments

Phosphate-lowering treatment, including low phosphate diet and phosphate binding therapy such as sevelamer hydrochloride, should be implemented prophylactically with meals on the first day of study drug initiation and modified as clinically indicated throughout Infigratinib administration. Recommendations for treatment are provided in **Table 6**, but should be modified as per country or institutional guidelines.

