Worst Toxicity CTCAE v5.0 Grade (unless otherwise specified)	Recommended Dose Modifications any time during a cycle of therapy
Laboratory / Metabolic disorders	
Asymptomatic amylase and/or lipase elevation	
Grade 3 (> 2.0 - 5.0 x ULN with signs or symptoms; >5.0 x ULN and asymptomatic)
 
 • Hold dose of Infigratinib until resolved to CTCAE Grade \leq 2. • ↓ 1 dose level of Infigratinib 
For recurrent Grade 3 asymptomatic lipase or amylase elevation despite dose reduction, drug should be held and continuation of therapy should be discussed with the medical monitor following resolution to \leq Grade 2.

Grade 4 (>5.0 x ULN and with signs and symptoms)	
For any Grade 4 asymptomatic lipase or amylase elevation, drug should be held and continuation of therapy should be discussed with the medical monitor following resolution to \leq Grade 2.

	
Note: A CT scan or other imaging study to assess the pancreas, liver, and gallbladder should be performed as clinically indicated within 1 week of the first occurrence of any CTCAE \geq Grade 3 amylase and/or lipase.

Hyperphosphatemia	
Grade 1: Laboratory finding only and intervention not indicated	
Maintain dose level of Infigratinib and optimize phosphate lowering therapy as clinically indicated.

Grade 2: Noninvasive intervention indicated	
Maintain dose level of Infigratinib and optimize phosphate lowering therapy as clinically indicated.

Grade 3: Severe or medically significant but not immediately life-threatening; hospitalization or prolongation of existing hospitalization indicated	
Hold Infigratinib until resolved \leq Grade 2. Restart at same dose level with maximal phosphate binder dosing.

Grade 4: Life-threatening consequences; urgent intervention indicated (e.g. dialysis)	
Hold Infigratinib until resolved \leq Grade 2. Reduce one dose level dose level with maximal phosphate binder dosing.

	
It is recommended that phosphate binder dosing continues during Infigratinib dose interruptions for hyperphosphatemia and that serum phosphorus values be monitored frequently, e.g. every 2-3 days.

	
Phosphate binder dosing should be held during the week off Infigratinib therapy each cycle (Days 22-28) and during Infigratinib dose interruptions for non-hyperphosphatemia adverse events.

Worst Toxicity CTCAE v5.0 Grade (unless otherwise specified)	Recommended Dose Modifications any time during a cycle of therapy

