6.3.1 Permitted concomitant therapy

Any palliative and supportive care for disease related symptoms, including any medication for a concurrent medical condition are permitted, except as specifically prohibited below.

Hematopoietic growth factors

Hematopoietic growth factors (e.g. erythropoietin, G-colony stimulating factor (CSF) and GM-CSF) are not to be administered prophylactically or to be used to meet eligibility criteria. However, these drugs may be administered as per the label of these agents or as dictated by local practice or guidelines established by the American Society of Clinical Oncology (ASCO).

Hormone replacement therapies

Hormone replacement therapies such as thyroid and growth hormones are allowed, as well as estrogen replacement hormone treatment.

Phosphate-lowering therapy

Phosphate-lowering treatment, including low phosphate diet and phosphate binding therapy, such as sevelamer hydrochloride, should be implemented prophylactically at study drug initiation and modified as clinically indicated throughout Infigratinib administration. Recommendations for treatment are provided in **Table 6**, but should be modified as per country or institutional practice.

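### Table 6 stops phosphate binders on Days 22-28 of every cycle, with no exception for Grade 3-4 hyperphosphatemia that is still unresolved

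*Combined protocol and SAP*

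**What the plan says.** The hyperphosphatemia block of Table 6 (Section 6.2.1) gives three instructions about binders.

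- **Hold for hyperphosphatemia:** "It is recommended that phosphate binder dosing continues during Infigratinib dose interruptions for hyperphosphatemia". The same sentence recommends frequent phosphorus checks, for example every 2-3 days.
- **Scheduled week off:** "Phosphate binder dosing should be held during the week off Infigratinib therapy each cycle (Days 22-28"). No condition is attached.
- **Hold for another reason:** the week-off sentence goes on, "and during Infigratinib dose interruptions for non-hyperphosphatemia adverse events". Only this limb is limited by cause.

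The Grade 3 and Grade 4 rows hold Infigratinib until Grade 2 or lower. They mention maximal binder dosing only in connection with the restart or dose reduction, and neither row says what happens if the event is unresolved on Day 22.

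Two other sections address phosphate-lowering therapy in general terms. Section 6.3.1 says it "should be implemented prophylactically at study drug initiation and modified as clinically indicated throughout Infigratinib administration", and Section 6.1.2 has similar wording. Both refer to Table 6 for recommendations and allow local guidelines or practice to modify them. Neither mentions the week off.

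**The concern.** Infigratinib is off during Days 22-28 for every patient, so a rule that stops binders in that week makes sense when phosphorus is controlled. It makes less sense when a severe event is still open, and Table 6 does not separate the two cases.

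The patients concerned have the most serious hyperphosphatemia. Table 6 describes Grade 3 as severe or medically significant, with "hospitalization or prolongation of existing hospitalization indicated", and Grade 4 as life-threatening. Section 1.2.1.3 links raised serum phosphorus in rats and dogs with mineralization of kidney, lung, vascular and digestive tissue that was only partly reversible. Those are animal data under repeated dosing and do not test what happens when binders stop after the drug is off. They explain why the protocol takes phosphate seriously, but they do not measure the harm from this wording.

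At stake is consistent management of a known toxicity across several centres. A site that follows the sentence to the letter would withdraw phosphate-lowering treatment during an unresolved severe event.

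**Working it through.** There is no planned figure to reproduce. The check compares the sentences in each situation, then counts days to see whether the situations can arise.

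**1. Which sentence applies?**

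| Situation | Continue-binders sentence | Week-off sentence | Result |
|---|---|---|---|
| A. Hold for Grade 3-4 hyperphosphatemia still running on Day 22 | Applies | Applies | Conflict; the table does not say which prevails |
| B. Grade 3-4 first found at about Day 21, no dose due until next cycle | Arguably does not apply | Applies | Gap; read literally, binders stop |

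Situation B turns on what counts as a dose interruption. Section 7.1.4 measures the length of an interruption from the day the next dose was scheduled. On that basis nothing is interrupted until a scheduled dose is missed. The 2-3 day phosphorus check sits in the continue-binders sentence, so it may lapse too. The next scheduled chemistry after Cycle 1 Day 21 is Cycle 2 Day 1, which is 29 - 21 = 8 days later.

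**2. Can situation A occur?** A hold of *d* days starting on Day *s* ends on Day s + d - 1. It reaches Day 22 if s + d - 1 ≥ 22, so the shortest such hold is d = 23 - s. For the chemistry days in Table 7:

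| Start of hold | Shortest hold reaching Day 22 |
|---|---|
| Day 21 (Cycle 1 only) | 23 - 21 = 2 days |
| Day 15 (Cycles 1 and 2) | 23 - 15 = 8 days |
| Day 8 (Cycle 1 only) | 23 - 8 = 15 days |

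From Cycle 3 on, chemistry is scheduled on Day 1 only, apart from end of treatment.

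The protocol gives no hold length for this schedule. The only documented duration comes from the phase 1 study: "the median time until first dose interruption was approximately 23 days and the median duration of interruption was 7 days" (Section 2.3). That was under continuous dosing, before prophylactic phosphate-lowering therapy. If a 7-day hold is assumed, start days from 23 - 7 = 16 to 21 qualify. Among the target chemistry days, only Cycle 1 Day 21 falls in that range.

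**3. Can situation B occur?** Yes. Table 7 schedules chemistry on Cycle 1 Day 21, the last dosing day. The general visit window in Section 7.1 is ±3 days, so the sample may be drawn as late as Day 24, inside the week off. A result that arrives after the Day 21 dose has the same effect.

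**4. How many patients?** The documents do not allow an estimate. Section 1.2.1.4.1 reports Grade 3-4 hyperphosphatemia in 15.9% of the cholangiocarcinoma study, without stating the grading used. Applied to 50 patients, that is 0.159 × 50 = 7.95 patients with such an event at any time. A count for Day 22 also needs the distribution of start days and of hold lengths under this schedule and with prophylactic binders. Neither is given. Section 2.3 points to a low number: most patients in the 3-weeks-on, 1-week-off expansion arm "completed their first cycle of therapy without hyperphosphatemia induced dose interruptions".

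**The case against.** The strongest reply is that the two sentences can be reconciled. One covers active hyperphosphatemia; the other covers the routine week off and unrelated interruptions. The specific instruction would naturally govern the general one, so a clinician would continue binders. Table 6 gives recommendations, and Sections 6.1.2 and 6.3.1 let them be adapted. Section 6.2.2 requires at least weekly follow-up for 4 weeks after an interruption for toxicity. Patients at these grades would be under hospital-level care. Limiting binders while the drug is off may also be deliberate: Section 1.2.1.4.1 reports hypophosphatemia in 27.0% of patients (6.3% Grade 3-4), although the protocol does not give this as the reason.

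Much of this stands. It gives situation A a likely answer and lowers the risk in both situations, but it does not close the gap:

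- The discretion is "modified as clinically indicated throughout Infigratinib administration", and whether that covers a week with no drug is arguable. The local-guideline wording is broader, but neither provision ranks the two sentences.
- Section 6.2.2 is also triggered by interruption or discontinuation of treatment, so its reach in situation B is uncertain for the same reason.
- The specific-over-general reading does not help in situation B if no interruption exists.

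A reader might go further and infer that the two sentences also contradict each other in situation B. The text does not support that: with no dose due, arguably only one of them applies.

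**Conclusion.** The point holds as a minor safety-management defect. The week-off sentence has no exception for unresolved Grade 3-4 hyperphosphatemia. It conflicts with the preceding sentence when a hold runs past Day 21, and it leaves a gap when the event is first found at about Day 21. The likely intent is to continue binders. The situation B finding depends on reading an interruption as a missed scheduled dose, which Section 7.1.4 suggests but Table 6 does not define.

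The number affected is probably very few. A reader might infer a figure such as 5 of 50 by taking 7.95 events, assuming 14-day holds and spreading start days evenly over Days 1-21: 7.95 × 13/21 = 4.92. The documents do not support that figure. They give no 14-day hold, the 15.9% is from another study with unstated grading, and even spacing does not match the chemistry schedule. The phase 1 median of about 23 days to first interruption lies near Day 22, but it came from continuous dosing before prophylaxis and does not predict timing here.

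Nor should a reader infer an effect on the trial's conclusions. The ORR analysis, the Cohort 1 two-stage design, the sample size and the error rates do not depend on this rule.

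**What to change.** Leave the existing sentence in Table 6 as it is, including the limb on non-hyperphosphatemia adverse events, and add one sentence after it:

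*Exception to the week-off hold: while Grade 3-4 hyperphosphatemia is unresolved, binders continue through Days 22-28 and serum phosphorus is checked about every 2-3 days, whether or not a dose is due.*

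The closing phrase covers the Day 21 case. The sponsor should define resolution. Grade 2 or lower would match the existing restart rule, but Table 6 describes Grade 2 as needing noninvasive intervention and advises optimizing phosphate-lowering therapy, so the sponsor should also say whether binders may stop in the week off at that grade.

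The cost is one sentence in the next amendment and no new scheduled visits. For a hold already under way, the phosphorus checks are already recommended. In the Day 21 case they may be new, which means a few extra blood tests in very few patients.

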Hypercalcemia Serum calcium Grade 2 or 3	Hold Infigratinib dose until resolved to Grade 1 or baseline: 
 if resolved within \leq 7 days after suspending Infigratinib, maintain dose level if resolved within $>$ 7 days after suspending Infigratinib, \downarrow 1 dose level
Serum calcium \geq Grade 4	Discontinue patient from the study
Nervous system disorders	
Neurotoxicity Grade 2	Omit dose of Infigratinib until resolved to CTCAE Grade \leq 1, then \downarrow 1 dose level of Infigratinib
Grade \geq 3	Discontinue patient from study drug treatment
GI disorders	
Pancreatitis Grade 2 (Enzyme elevation; radiologic findings only)	Hold Infigratinib dose until resolved to Grade 1 or baseline: 
 if resolved within \leq 7 days after suspending Infigratinib, maintain dose level if resolved within $>$ 7 days after suspending Infigratinib, \downarrow 1 dose level
Grade \geq 3 (Severe pain; vomiting; medical intervention indicated)	Discontinue patient from study drug treatment
Diarrhea Grade 1	Maintain dose level of Infigratinib, initiate anti-diarrheal treatment
Grade 2	
 Hold dose of Infigratinib until resolved to CTCAE Grade \leq 1 Optimize anti-diarrheal treatment, maintain dose level of Infigratinib. For reoccurrence of diarrhea CTCAE Grade 2, hold dose of Infigratinib until resolved to CTCAE Grade \leq 1, \downarrow Infigratinib by 1 dose level

Worst Toxicity CTCAE v5.0 Grade (unless otherwise specified)	Recommended Dose Modifications any time during a cycle of therapy
Grade 3	
 • Hold dose of Infigratinib until resolved to CTCAE Grade \leq 1 • Optimize anti-diarrheal treatment • \downarrow Infigratinib by 1 dose level • For reoccurrence of diarrhea CTCAE Grade 3, despite optimal antidiarrheal treatment, discontinue patient from study treatment.
Grade 4	
Discontinue patient from study treatment.
 
Note: Antidiarrheal medication is recommended at the first sign of abdominal cramping, loose stools or overt diarrhea

Vomiting Grade 2 not controlled by optimal anti-emetic therapy Grade 3 not controlled by optimal anti-emetic therapy or Grade 4	Hold Infigratinib doses until \leq Grade 1, \downarrow 1 dose level Discontinue patient from study
Eye Disorders (confirmed by ophthalmologic examination)	

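### Table 6's amylase/lipase and pancreatitis rows overlap, and the worst-toxicity rule leaves the restart grade and the action for symptomatic patients unresolved

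*Combined protocol and SAP*

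**What the plan says.** Two rows of Table 6 (Section 6.2.1) deal with pancreatic events.

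- **Enzyme row**, under laboratory/metabolic disorders, headed "Asymptomatic amylase and/or lipase elevation". Its Grade 3 is "Grade 3 (> 2.0 - 5.0 x ULN with signs or symptoms; >5.0 x ULN and asymptomatic". The action is "Hold dose of Infigratinib until resolved to CTCAE Grade" 2 or lower, followed by a downward arrow and "1 dose level of Infigratinib", with no condition on time to recovery. Its Grade 4 is a rise above 5 x ULN with signs and symptoms. The action there is to hold and to discuss continuation with the medical monitor once the event is back to Grade 2 or lower. A note adds: "A CT scan or other imaging study to assess the pancreas, liver, and gallbladder should be performed as clinically indicated within 1 week" of a first elevation of Grade 3 or higher.
- **Pancreatitis row**, under GI disorders. The first entry is "Pancreatitis Grade 2 (Enzyme elevation; radiologic findings only": hold to Grade 1 or baseline, then the same dose level if that took 7 days or less, or one level down if it took longer. The second entry is Grade 3 or higher, described as "Severe pain; vomiting; medical intervention indicated": discontinue study drug.

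Two general rules bear on both rows. The text of Section 6.2.1 and the closing note of Table 6 both base dose modifications on the worst preceding toxicity. Section 6.2.1 also describes resumption after recovery to baseline or Grade 1 or lower, at the dose that Table 6 indicates.

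**The concern.** The enzyme row's own note may send a patient for pancreatic imaging, and a positive result places that patient in the pancreatitis row as well. The two rows then set different conditions for restarting and, in some cases, different actions. Nothing in either row excludes the other. Elsewhere Table 6 does draw such a line: the AST/ALT entries are limited to patients without a bilirubin rise above 2 x ULN, and the combined abnormality has its own row.

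Two things are at stake. The first is safety: staff at different sites could handle the same presentation differently and each point to the table. The second is measurement. Dose interruptions, reductions and dose intensity are the tolerability endpoints in Table 3 and are summarized under Section 10.3. Where the table can be read two ways, these endpoints partly record the site's reading. They are secondary and descriptive, and nothing here shows an effect on the primary response-rate analysis.

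**Working it through.** The plan gives no figure of its own to reproduce on this point. The check sets the two rows side by side for each presentation and then applies the worst-toxicity rule. I rank by CTCAE grade, because the left column of Table 6 is headed by worst CTCAE grade.

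| Presentation | Enzyme row | Pancreatitis row | What the rule settles |
|---|---|---|---|
| A. No symptoms, enzymes up to 5 x ULN, radiologic findings | No entry | Grade 2 | No conflict |
| B. No symptoms, above 5 x ULN, no radiologic findings | Grade 3: hold to Grade 2 or lower, one level down | Not met, if enzyme rise and imaging are both required | No conflict on that reading |
| C. No symptoms, above 5 x ULN, radiologic findings, recovery within 7 days | Grade 3: hold to Grade 2 or lower, one level down | Grade 2: hold to Grade 1 or baseline, same dose | Dose: Grade 3 outranks Grade 2, so one level down. Restart grade: open |
| D. As C, recovery after more than 7 days | As C | Grade 2: hold to Grade 1 or baseline, one level down | Dose: rows agree. Restart grade: open |
| E. Enzymes above 2 to 5 x ULN with symptoms; pancreatitis Grade 3 | Grade 3: hold, one level down | Grade 3: discontinue | Tie: rule cannot choose |
| F. Enzymes above 5 x ULN with signs and symptoms; pancreatitis Grade 3 | Grade 4: hold, discuss with medical monitor | Grade 3: discontinue | Grade 4 outranks Grade 3, which displaces the discontinuation |

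Remarks on the cases:

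1. **C and D, restart grade.** A patient who has come down to Grade 2 may restart under the enzyme row and must still hold under the pancreatitis row. The general text of Section 6.2.1 gives a third statement (baseline or Grade 1 or lower) but refers to Table 6 for the resumption criteria. The worst-toxicity rule does not say whether the other row's recovery condition must also be met.
2. **B.** The pancreatitis entry joins its two elements with a semicolon. If they are alternatives, B overlaps as well.
3. **E and F.** The row is headed as asymptomatic, yet symptoms define part of its Grade 3 and all of its Grade 4. Its Grade 4 action then speaks of asymptomatic elevation, a patient whom its Grade 4 definition excludes. The heading therefore cannot settle whether a symptomatic patient belongs in the row.

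**Frequency.** Section 1.2.1.4.1 reports Grade 3 or 4 lipase increase in 7.9% of patients in the cholangiocarcinoma study. With 50 patients planned:

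- Expected number: 50 x 0.079 = 3.95, about 4 (binomial 90% range 1 to 7).
- Probability of at least one: 1 - 0.921^50 = 1 - 0.016 = 0.984.

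The documents do not give the share who also have radiologic findings. If it were 10% to 50% (assumption), 3.95 x 0.10 = 0.40 to 3.95 x 0.50 = 1.98 patients would meet both rows. The probability of at least one would be 1 - (1 - 0.0079)^50 = 0.33 to 1 - (1 - 0.0395)^50 = 0.87. The restart-dose texts differ only in case C, which also needs recovery within 7 days. If half recovered that fast (assumption), 0.20 to 0.99 patients would be affected. Even that treats every case as asymptomatic, and the 7.9% is not split by symptoms or by grade.

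**The case against.** The strongest reply is that the protocol already has a tie-breaker, stated twice, and that it works in the main case. A Grade 3 enzyme rise with Grade 2 pancreatitis is governed by the Grade 3 entry, so the dose goes down one level. This stands. A reader who compares only the two rows might infer that no text says which governs, that the instructions are opposite, or that a positive scan removes the dose reduction. The documents do not support these readings. The Grade 3 laboratory finding is still present and still the worst grade, asymptomatic rises up to 5 x ULN have no entry in the enzyme row, and beyond 7 days both rows reduce.

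A second reply is that the recovery conditions are compatible, because a patient at Grade 1 or baseline is also at Grade 2 or lower. A cautious site can indeed satisfy both. But the enzyme row, which the rule selects, permits restart earlier, and no text says that the stricter condition survives.

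A third reply is that the enzyme row's heading keeps symptomatic patients out, which would leave severe pain or vomiting to the pancreatitis row alone. This fails on the row's own wording, since its grade text includes ">5.0 x ULN and asymptomatic" as only one part of Grade 3 and defines the rest by signs or symptoms.

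Imaging is also only as clinically indicated, so not every Grade 3 enzyme rise will be tested for overlap. That limits the frequency but does not remove the conflict.

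**Conclusion.** The two rows overlap, and the worst-toxicity rule resolves the overlap only in part. It settles the dose step for the asymptomatic patient above 5 x ULN with radiologic findings. It leaves the restart grade open for that patient, cannot break the Grade 3 tie between reducing and discontinuing, and at Grade 4 enzymes displaces the discontinuation instruction for Grade 3 pancreatitis. The mismatch between the row's heading and its grades adds to the uncertainty.

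A reader might also infer that one event can lead to same-dose restart, reduced dose or permanent discontinuation. It cannot: same-dose restart belongs to pancreatitis with radiologic findings only, and discontinuation to pancreatitis with severe pain, vomiting or medical intervention. These are different presentations.

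The size is small in patient numbers. About 4 of 50 would have a Grade 3 or 4 lipase increase if the earlier rate carries over to this mixed-tumor population. The share meeting both rows is unknown, and the share facing different dose text is smaller still. The conclusion rests on ranking toxicities by CTCAE grade and on reading the Grade 2 pancreatitis entry as enzyme rise plus imaging. It should be corrected because it concerns safety instructions and is cheap to repair. I take no view on which dose or recovery rule is right.

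**What to change.** Reconcile the general text of Section 6.2.1, the enzyme row, the pancreatitis row and the closing note of Table 6. Either of two routes would do:

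- make the two rows mutually exclusive by stated criteria, such as imaging result and symptoms, as the table already does for AST/ALT with and without bilirubin elevation; or
- state which row governs when both are met, for the restart grade and the dose action separately, including equal grades and Grade 4 enzymes with Grade 3 pancreatitis.

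In either case, align the enzyme row's heading and its Grade 4 action with its grade definitions, and say whether the two elements of the Grade 2 pancreatitis entry are both required. The clinical content of each instruction is for the sponsor's medical team to decide.

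The cost is a wording amendment to Table 6 and the related text of Section 6.2.1. It adds no procedure, because the imaging note is already in the table, and it leaves the sample size and the analysis unchanged.

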Febrile neutropenia Grade 3 (ANC $< 1.0 \times 10^9/L$, single temperature of $> 38.3^{\circ}C$ or 101F, or a sustained temperature of $\geq 38.0^{\circ}C$, or 100.4F)	Hold dose of Infigratinib until resolved to CTCAE Grade \leq 1, then: 
 • If resolved within \leq 7 days, \downarrow 1 dose level of Infigratinib. • If not resolved within 7 days discontinue patient from study drug treatment. Grade 4
Hemoglobin Grade 3 (<8.0 mg/dL, transfusion indicated)	Hold dose of Infigratinib until resolved or corrected to CTCAE Grade \leq 1 or baseline, then maintain dose level
	Grade 4 (Life-threatening consequences; urgent intervention indicated)
	Hold dose of Infigratinib until resolved or corrected to CTCAE Grade \leq 1 or baseline, then \downarrow 1 dose level

Worst Toxicity CTCAE v5.0 Grade (unless otherwise specified)	Recommended Dose Modifications any time during a cycle of therapy
Platelet count decreased (Thrombocytopenia)	
Grade 3 (PLT < 50 - 25 x 10 ⁹ /L) without bleeding	
Hold dose of Infigratinib until resolved to CTCAE Grade ≤ 1 or baseline
 
 • If resolved within ≤ 7 days, maintain dose level of Infigratinib. • If resolved within > 7 days, ↓ 1 dose level of Infigratinib
Grade 3 (PLT < 50 - 25 x 10 ⁹ /L) with bleeding or Grade 4 (PLT < 25 x 10 ⁹ /L)	Hold dose of Infigratinib until resolved to CTCAE Grade ≤ 1 or baseline, then ↓ 1 dose level
Investigations – Renal	
Serum creatinine ≥ Grade 2	
Grade 2 (> 1.5 - 3.0 x ULN or baseline)	
If serum creatinine CTCAE Grade ≥ 2 has been demonstrated in conjunction with hyperphosphatemia, serum creatinine levels must be repeated at least weekly until resolution. 24-hour urine collection should be obtained as clinically indicated for total phosphate, calcium, protein, and creatinine clearance. Ultrasound examination of the kidneys should be performed as indicated to evaluate de-novo calcifications until resolution or stabilization of creatinine.

Grade ≥ 3 (> 3.0 x baseline; >3.0-6.0 x ULN)	
Hold dose of Infigratinib until resolved to Grade ≤1 or baseline:
 
 • If resolved within ≤ 7 days, maintain dose level of Infigratinib. • If resolved within > 7 days, ↓ 1 dose level of Infigratinib.
Grade ≥ 3 (> 3.0 x baseline; >3.0-6.0 x ULN)	
Discontinue patient from study treatment.	
Investigations – Hepatic	

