Retinal disorders Grade 2 central serous retinopathy and central serous retinopathy -like events Grade 3 central serous retinopathy and central serous retinopathy-like events and any other Grade 3 eye disorders \geq Grade 1 retinal vein occlusion, Grade 4 central serous retinopathy and central serous retinopathy-like events, and Grade 4 other eye disorders	Hold Infigratinib until resolved to \leq Grade 1 and continue ophthalmologic evaluation 
 • If resolved within \leq 14 days, \downarrow Infigratinib by 1 dose level • If resolved within $>$ 14 days, discontinue Infigratinib Hold Infigratinib until resolved to Grade \leq 1. 
 • If resolved within \leq 14 days, \downarrow Infigratinib by 1 dose level • If resolved within $>$ 14 days, discontinue Infigratinib Discontinue Infigratinib
Other ocular/visual toxicity \geq Grade 3	Hold Infigratinib until resolution to \leq Grade 1 If resolution within \leq 14 days, \downarrow 1 dose level, otherwise discontinue Infigratinib
General disorders	

Worst Toxicity CTCAE v5.0 Grade (unless otherwise specified)	Recommended Dose Modifications any time during a cycle of therapy
Fatigue Grade 3	Hold dose of Infigratinib until resolved to CTCAE Grade ≤ 1. If resolved within ≤ 7 days, maintain dose level of Infigratinib.
Other clinically significant AEs	
Grade 3	Hold dose of Infigratinib until resolved to CTCAE Grade ≤ 1, then ↓ 1 dose level of Infigratinib.
Grade 4	Discontinue patient from study treatment.
All dose modifications should be based on the worst preceding toxicity. Once a dose reduction has occurred dose re-escalation may be allowed on a case by case basis after discussion with the Principal Investigator/Sponsor. Patients who require more than two dose reductions of Infigratinib will be generally discontinued from study drug treatment.	

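### Table 6 gives two different recommended actions for a Grade 4 non-retinal eye toxicity that resolves within 14 days; the last eye row should be limited to Grade 3

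*Combined protocol and SAP*

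**What the plan says.** The eye block of Table 6 (Section 6.2.1) has two rows.

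- The first is headed as retinal disorders and has three triggers with three actions in the same order. The second trigger covers Grade 3 central serous retinopathy and "any other Grade 3 eye disorders": hold, reduce one level if resolved within 14 days, otherwise discontinue. The third covers retinal vein occlusion of any grade together with "Grade 4 central serous retinopathy and central serous retinopathy-like events, and Grade 4 other eye disorders". Its action is to discontinue, with no hold and no 14-day window.
- The second row is "Other ocular/visual toxicity \geq Grade 3". The drug is held until the event is Grade 1 or less. If that takes no more than 14 days, the action is a reduction of "1 dose level, otherwise discontinue Infigratinib".

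The column of actions is headed as recommended modifications. The footnote to Table 6 bases every modification on the worst preceding toxicity, and adds: "Patients who require more than two dose reductions of Infigratinib will be generally discontinued from study drug treatment". The body of Section 6.2.1 allows three reductions, and allows treatment to continue past a stopping rule in exceptional situations after discussion with the Principal Investigator.

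**The concern.** Grade 3 or higher includes Grade 4. A Grade 4 eye toxicity outside the retina, a corneal event for example, fits the third trigger of the first row and also fits the second row. If it resolves within 14 days, one row stops the drug and the other permits re-exposure at a lower dose. In a multi-center trial, two sites could treat the same event differently and each be following the table. Under the discontinue entry, a restart needs a case-by-case discussion with the Principal Investigator. Under the last row it does not. What is at stake is therefore whether central discussion comes before re-dosing after a Grade 4 eye event.

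**Working it through.** No plan figure is involved, so the check sets the entries side by side.

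**Step 1: where the two rows differ (non-retinal eye toxicity).**

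| Event | First eye row | Last eye row | Same action? |
|---|---|---|---|
| Grade 3, resolved within 14 days | one level lower | one level lower | yes |
| Grade 3, not resolved within 14 days | discontinue | discontinue | yes |
| Grade 4, not resolved within 14 days | discontinue | discontinue | yes |
| Grade 4, resolved within 14 days | discontinue | one level lower | **no** |

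The overlap is limited to the last line.

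**Step 2: is there a rule of precedence?** None was found.

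- The worst-toxicity footnote fixes the grade to use, not the row.
- The exception in Section 6.2.1 waives stopping rules case by case and does not rank rows.
- Section 7.1.4 requires stopping for an adverse event with significant risk and names no row.
- Section 7.2.2.5 covers only the eye examinations.
- Section 8.3.2 sets up safety review and does not interpret the table.

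**Step 3: what does the rest of Table 6 do at Grade 4?**

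- Non-laboratory toxicities: other cardiac disorders (Grade 3 or higher), neurotoxicity (Grade 3 or higher), pancreatitis (Grade 3 or higher), diarrhea (Grade 4), vomiting (Grade 4) and the catch-all row for other clinically significant events (Grade 4) all discontinue. The Grade 4 febrile neutropenia action cannot be read in the available text and is not counted.
- Laboratory values: restart one level lower is allowed after low platelets ("with bleeding or Grade 4"), Grade 4 hemoglobin, and Grade 4 hyperphosphatemia ("Reduce one dose level dose level with maximal phosphate binder dosing"). Grade 4 amylase or lipase elevation goes to discussion with the medical monitor. Grade 4 AST or ALT, bilirubin, creatinine and calcium discontinue, apart from bilirubin elevation due to hemolysis.

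Outside the disputed row, no legible non-laboratory Grade 4 entry allows a routine restart.

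**Step 4: size per event.** The Table 5 levels are 125, 100, 75 and 50 mg. The discontinue entry gives 0 mg. The restart row gives:

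- from 125 mg: 100 mg, and 100/125 = 80% of the starting dose;
- from 100 mg: 75 mg, and 75/125 = 60%;
- from 75 mg: 50 mg, and 50/125 = 40%. This is a third reduction. Section 6.2.1 allows three, but also lists the third among its exceptional situations, and the Table 6 footnote generally discontinues at that point;
- from 50 mg: no lower level exists, so the two rows no longer differ in effect.

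The difference is thus full at 125 and 100 mg and limited at 75 mg. The documents give no Grade 4 ocular rate, so no expected count can be stated.

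**The case against.** There are two ways to read the overlap away. The first row's retinal heading could confine its Grade 4 entry to retinal events, leaving other Grade 4 events to the last row. But the entry speaks of eye disorders, the term used for the whole block, and not of retinal disorders. Alternatively, the last row opens with the word other, so it can be taken as residual. Grade 4 eye disorders are already named above it, so they would discontinue. That leaves the last row almost nothing to do. The two readings point in opposite directions, and neither is written down.

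The stronger objection is about consequence, and most of it stands. Section 7.1.4 makes stopping mandatory when an adverse event carries significant risk, so a site would first have to judge that a Grade 4 eye event did not. Section 6.2.2 requires at least weekly follow-up during an interruption, with specialist input as needed. Section 8.2.2.2 gives 24-hour notice of a serious event. Section 8.3.2 adds a mandatory monthly safety teleconference for all sites and review of serious events by the monitoring committee. These controls limit harm and divergence between sites, but they do not choose a row.

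A reader might infer from the Grade 4 restarts elsewhere in Table 6 that the intended action here is wide open. The table does not support that, because those restarts are all for laboratory values. A reader might also infer that the last row obliges a site to re-dose. It does not, because the entries are recommendations.

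**Conclusion.** The overlap is real and narrow: a Grade 4 non-retinal eye toxicity, resolved to Grade 1 or less within 14 days, in a patient above 50 mg. No text settles which row applies, though the pattern of the table favors discontinuation.

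Severity is minor. Section 1.2.1.4.1 describes ocular events as frequent but generally mild to moderate and reversible, and Section 5.3 excludes current corneal or retinal disorder, so the case should be rare. Whether a Grade 4 eye event can recover this fast depends on grading definitions that the protocol does not reproduce. The conclusion assumes that the three triggers and three actions of the first row pair in order, which is the only arrangement that makes sense of them.

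It would be wrong to infer a threat to the efficacy results. The overall response rate analysis and the Cohort 1 two-stage design do not depend on which row is followed.

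**What to change.** Change the last eye row from Grade 3 or higher to Grade 3 only, so that every Grade 4 eye toxicity leads to discontinuation. Deleting the row would also work, since at Grade 3 it duplicates the entry for "any other Grade 3 eye disorders". Limiting it is slightly safer. A site that takes the retinal heading literally would then fall to the catch-all Grade 4 row, which also discontinues, and non-retinal Grade 3 events would keep their 14-day limit.

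Removing the Grade 4 eye wording from the discontinue entry instead is not advised. It would also drop the stopping rule for Grade 4 retinal events other than central serous retinopathy or vein occlusion.

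Any continuation would go through the Section 6.2.1 exception. Neither example listed there is a Grade 4 eye event, but the list is not exhaustive. The downside is that a rare patient whose Grade 4 eye event resolves quickly could restart only by that route. The cost is one row edit in the next amendment, with no change to data collection, sample size or analysis.
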